7.4. Individual and Study Stopping Rules

7.4.1. Subject Discontinuation from Study Drug

A subject will be permanently withdrawn from study drug for any of the following reasons:

- Subject request to discontinue for any reason.
- Pregnancy in a female subject.
- Emergence of an AE, including a laboratory abnormality, or other unacceptable toxicity that, in the judgment of the investigator, compromises the ability of the subject to continue study-specific procedures or it is considered not to be in the subject's best interest to continue due to an altered benefit-risk profile.
- Intercurrent illness or the emergence of a new medical condition that would, in the judgment of the investigator, affect assessments of clinical status to a significant degree.
- Treatment-emergent ALT $> 3 \times$ upper limit of normal (ULN) (confirmed by repeat testing) combined with either:
 - laboratory abnormalities indicative of significant hepatic toxicity (ie, meeting Hy's law, total bilirubin $> 2 \times$ ULN or with a new increase in INR > 1.5 in the absence of warfarin therapy)

OR

- symptomatology of acute hepatitis (ie, severe fatigue, nausea, vomiting, right upper quadrant pain and tenderness, fever, rash, and/or eosinophilia [$> 5\%$] that has not been part of the subject's history of PNH symptomatology)

AND

- assessed as probably or definitely related to BCX9930

AND

- without clinical and/or laboratory evidence of hemolysis or any other potential alternative etiology.
- Treatment-emergent increase in sCr $\geq 3 \times$ ULN (confirmed by repeat testing) without clinical and/or laboratory evidence of hemolysis or any other potential cause of renal dysfunction.
- Invasive meningococcal infection or invasive encapsulated bacterial infection. Discontinuation of BCX9930 may occur after subject stabilization to prevent uncontrolled hemolysis.
- In the investigator's opinion it is in the best interest of the subject to discontinue from further dosing.
- Subject noncompliance (eg, protocol deviation), as assessed by the sponsor or investigator, to be detrimental to study or subject benefit-risk profile.
- Discontinuation at the request of the sponsor, relevant competent authority, or the governing institutional review board (IRB), research ethics board (REB), or independent ethics committee (IEC), collectively referred to as "ethics committee".

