11. STUDY CONDUCT

11.1. Overview

This is an open-label, non-randomized study to evaluate the long-term safety and effectiveness of daily oral BCX9930.

Subjects will be eligible to receive study drug (BCX9930) for up to 144 weeks, until drug is available by another mechanism (eg, expanded or market access) or until the Sponsor discontinues development of the product for PNH (See Section 7.4), whichever comes first. Study drug will be discontinued for subjects who are deriving no clinical benefit, are intolerant of study drug, or experience an unacceptable drug-related TEAE as defined in more detail in Section 7.4. The Study will be discontinued if ongoing regulatory or Institutional Review Board/Ethics Committee (IRB/EC) approval is withdrawn, or in the event that technical or logistical factors prevent the ongoing conduct of the study. Subjects who discontinue study drug will have a minimum of 3 days hemolysis testing and then return to the clinic for an end-of-study visit 3 weeks after the last dose of study drug.

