14.3.5. Analysis of Safety Variables

Safety endpoints that will be summarized, at a minimum, include the proportion of subjects 1) with TEAEs; 2) who discontinue BCX9930 due to TEAEs; 3) with treatment-emergent SAEs; 4) with treatment-emergent Grade 3 or 4 AEs; and 5) with treatment-emergent Grade 3 or 4 laboratory abnormalities. In addition, the proportion of subjects who received a reduced dose due to tolerability issues at the full dose will be summarized.

Time to dose reduction, time to discontinuation due to a TEAE, and time to development of drug-related rash will be estimated using the Kaplan-Meier method. For those with a drug-related rash, clinical and laboratory findings will be summarized and the proportion of subjects who successfully continued therapy following onset of rash.

AEs will be mapped to a Medical Dictionary for Regulatory Activities (MedDRA) preferred term and system organ class (SOC). The occurrence of TEAEs will be summarized using MedDRA preferred terms, SOCs, and severity. Separate summaries of TEAEs, treatment-emergent SAEs, AEs considered related to study drug, and AEs leading to study drug interruption will be generated. All AEs will be listed for individual subjects showing both verbatim and preferred terms.

Descriptive summaries for vital signs, weight, bedside ECG parameters, and clinical laboratory results will be presented. Laboratory abnormalities will be graded according to the DMID Adult Toxicity Table (Publish Date: Draft, November 2007; Appendix 1).

Any graded abnormality that occurs following the initiation of study drug and represents at least 1-grade increase from the baseline assessment is defined as treatment emergent. The number and percentage of subjects experiencing treatment-emergent graded toxicities will be summarized. Laboratory toxicity shifts from baseline to worst post-baseline assessments will be summarized.

The number and percentage of subjects having elevations in liver enzyme abnormalities (ALT, AST, or bilirubin) in relation to fold above ULN will be summarized according to the Premarketing Clinical Evaluation on Drug-Induced Liver Injury Guidance for Industry.

Clinically significant abnormal morphological ECG findings will be summarized.

The change from baseline in QTcF will be determined by routine ECGs. At each time point ECGs are analyzed, an individual subject's change from baseline will be calculated as:

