#### **Duration of Treatment:**

Subjects will be eligible to receive study drug (BCX9930) for 144 weeks, or until drug is available by another mechanism (eg, expanded or market access) or until the Sponsor discontinues development of the product for PNH; whichever comes first.

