## 3.7. Clinical Assessments

Planned study visits are Screening; Day 1; Weeks 4 through 96 at 4-week intervals, and Weeks 104 through 144 at 8-week intervals. Safety and tolerability will be evaluated through assessments of TEAEs, laboratory analyses (clinical chemistry, hematology, coagulation, and urinalysis), vital signs, ECGs, and physical examinations at the study visits indicated in the schedule of assessments (see Table 2).

- The questionnaires are to be administered first, then physical exam, then ECG and vital signs before lab samples, PNH clone sample, then PK, PD, concomitant medication and AE review, PNH symptoms assessment, transfusion review, and finally drug dispensing.
- A site is permitted to perform screening assessments over more than one screening visit. Rescreening of ineligible subjects will be approved or denied on a case-by-case basis by the Sponsor Medical Monitor. Retesting of specific assessments without entirely rescreening a subject may be permitted. A screening failure electronic case report form (eCRF) page will be completed for those subjects who do not proceed with study dosing.
- Subjects who dose escalate (under Protocol versions 1-3) will have an additional Dose Escalation visit 2 weeks (± 2 days) after each dose increase.
- Following discontinuation of study drug (either following completion of the treatment period or on premature discontinuation), subjects will return to the clinic for a minimum of 3 consecutive days for Hemolysis Monitoring visits. Following the 3 days of monitoring, if required, subjects may continue to be assessed every 2 days thereafter until the subject has stabilized to a new hemoglobin baseline.
- Subjects who permanently discontinue treatment will return to the clinic for Hemolysis Monitoring visits. Subsequently they will return to the clinic 3 weeks (21 ± 3 days) after the date of their last dose of BCX9930 for their End of Study assessments.

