Time to first dose reduction either associated with an AE or otherwise, time to discontinuation due to a TEAE, and time to development of drug-related rash will be estimated using the Kaplan-Meier method. Subjects who do not experience a particular event will be censored at the date of the last study visit.

Clinical findings for cutaneous eruptions requiring assessment will be listed.

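### The Kaplan-Meier curves for TEAE discontinuation and first dose reduction give a net probability at or above the proportion of subjects with the event; cumulative incidence should be reported

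*SAP*

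**What the plan says.** SAP 9.1 lists "Time to first dose reduction either associated with an AE or otherwise, time to discontinuation due to a TEAE" among the endpoints to be estimated by Kaplan-Meier, and its only censoring instruction is "Subjects who do not experience a particular event will be censored at the date of the last study visit". Protocol 14.3.5 names the same estimator: "Time to dose reduction, time to discontinuation due to a TEAE, and time to development of drug-related rash will be estimated using the Kaplan-Meier method". Both synopses repeat it. Rash is outside this point. Neither document mentions competing risks or cumulative incidence.

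Subjects can leave treatment for individual reasons that are not TEAEs. Protocol 7.4.1 includes "Subject request to discontinue for any reason", "Pregnancy in a female subject" and noncompliance, and Protocol 11.1 adds "Study drug will be discontinued for subjects who are deriving no clinical benefit". After a permanent stop and hemolysis monitoring, SAP 3.7 gives the final visit: "Subsequently they will return to the clinic 3 weeks (21 ± 3 days) after the date of their last dose of BCX9930". That visit is the censoring date for a subject who completes follow-up.

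Treatment can also end for administrative reasons. The SAP synopsis allows 144 weeks, access by another mechanism, or "until the Sponsor discontinues development of the product for PNH".

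Other displays bear on the same quantities. SAP 9 plans the proportion discontinuing because of TEAEs, and Table 14.3.2.6 breaks those events down by system organ class and preferred term. Under SAP 5.4, percentages use all subjects in the group unless otherwise specified. For dose reduction, Protocol 14.3.5 and the SAP synopsis promise a proportion reduced for tolerability. The SAP 9 list omits it, and Table 7 has only the Kaplan-Meier table and figure (14.3.2.10) and total time on dose level (14.2.4).

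**The concern.** Kaplan-Meier treats a censored subject as having the same future risk as those still followed. That suits a subject whose observation simply ends, for example at Week 144. It does not describe a subject who has permanently stopped the drug at her own request: she cannot later stop because of a TEAE or have her dose reduced. For dose reduction, a stop because of a TEAE without a prior reduction has the same effect.

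Censoring these subjects passes their share of risk to those who remain, so 1-KM rises above the fraction of subjects who have the event. The primary endpoint is framed as incidence among subjects, and SAP 3.3 puts estimation ahead of testing. The natural question is therefore what fraction of enrolled subjects stop, or have the dose reduced, by a given week. The planned curves answer a different one: what the risk would be if nobody could stop for any other reason.

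**Working it through.** The plan states no event rate, dropout rate or sample size calculation, so there is no figure of its own to reproduce. All rates below are assumptions.

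**Inputs.** Horizon T = 144 weeks (SAP synopsis). N = 200, the approximate planned number (SAP 3.5). Lag from last dose to censoring = 3 weeks (SAP 3.7). Assumed: constant cause-specific hazards and no administrative censoring before Week 144. Let p1 be the true cumulative incidence of the event at Week 144 and p2 that of other-reason stops.

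**Direction, by a small example.** Take 20 subjects: 8 stop for other reasons and are censored, then 2 have the event.
- 1-KM = 1 - (11/12)(10/11) = 16.7%.
- Proportion with the event = 2/20 = 10%.

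The two agree only when no individual other-reason stop leaves the risk set before a later event.

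**Formulas.**
- Total cumulative hazard over T: H = -ln(1 - p1 - p2). Event part: H1 = H × p1/(p1 + p2).
- Censoring at last dose: 1-KM = 1 - exp(-H1).
- SAP rule: the hazard seen in the risk set at time t is l1·S(t)/[S(t) + C(t)]. Here l1 = H1/T, S(t) = exp(-Ht/T), and C(t) is the fraction who stopped for other reasons in the preceding 3 weeks. 1-KM is 1 minus the exponential of minus its integral over 0 to T, evaluated numerically.
- Standard error of the true proportion: sqrt[p1(1 - p1)/N] = sqrt(0.10 × 0.90/200) = 2.12 points.

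**Worked line, p1 = 10%, p2 = 30%.** H = -ln(0.60) = 0.5108. H1 = 0.5108 × 0.25 = 0.1277. 1 - exp(-0.1277) = 12.0%. Under the SAP rule it is 11.9%.

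**Results for a true 10%, N = 200.**

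| Other stops | H | 1-KM, censored at last dose | 1-KM, SAP rule | Excess, SAP rule (points) | Excess / SE |
|---|---|---|---|---|---|
| 10% | 0.2231 | 10.6% | 10.5% | 0.53 | 0.25 |
| 20% | 0.3567 | 11.2% | 11.2% | 1.16 | 0.55 |
| 30% | 0.5108 | 12.0% | 11.9% | 1.90 | 0.90 |
| 40% | 0.6931 | 12.9% | 12.8% | 2.81 | 1.32 |

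**Half-SE point.** With p2 = 18%, H = -ln(0.72) = 0.3285 and H1 = 0.3285 × 10/28 = 0.1173. 1-KM is 11.07%, an excess of 1.07 points against half an SE of 1.06.

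**Other true incidences, SAP rule, other stops 10% to 40%.** A true 5% gives 5.3% to 6.4%. A true 20% gives 21.1% to 26.0%.

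**Simulation check (2,000 trials of 200, censoring 3 weeks after last dose).** 10% with 20% other stops: mean 1-KM 11.2%. 10% with 40%: 12.8%. 20% with 30%: 24.1%. Each agrees with the integration.

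**By C5-inhibitor category.** Assuming an even split, n = 100 and the SE at 10% is 3.0 points. With 30% other stops the excess is 1.90/3.0 = 0.63 SE.

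**The case against.** The best defense has four parts.

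**Kaplan-Meier estimates something legitimate.** Under independent censoring it is a valid net risk, and for a safety endpoint it errs toward showing more harm. That stands. A reader might infer that the curves are invalid, or that the SAP will report 1-KM as the proportion affected. The documents support neither: SAP 9.1 does not say how the curves will be read, and no stopping rule or success criterion uses them.

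**The proportion is already planned.** This is partly right. The crude TEAE-discontinuation percentage equals the cumulative incidence when everyone is followed to 144 weeks or to an earlier stop. It falls below the 144-week incidence if sponsor closure or access by another mechanism cuts follow-up short, which the plan allows. For dose reduction no crude table is listed.

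**The size is supposition.** This stands. Eligibility requires benefit and completed dosing in the prior study, so a reader should not infer that 30% to 40% will stop for other reasons. Protocol 5.4.1 reports no discontinuations due to drug-related TEAEs, but that gives no rate for other stops.

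**A simple competing-risk rule has its own traps.** This also stands. Treating every death as competing would remove fatal TEAEs from a safety endpoint. The dose-reduction endpoint covers reductions for any reason, so it is not a safety-only curve. As worded it might count the move to 400 mg BID described in SAP 3.6, or a taper at discontinuation (Protocol 10.5.2 and Table 6). A tapered stop could then be an event rather than a competing one.

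A reader might also take the 3-week wait before censoring as a second fault. It slightly reduces the excess, from 12.9% to 12.8% at 10% incidence with 40% other stops.

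**Conclusion.** The point holds as a matter of estimand and labeling. With individual other-reason stops censored, 1-KM for both endpoints is a net probability at or above the proportion of subjects with the event. The direction needs no assumed rate. The size does: at a true 10% it is about 0.5 to 2.8 points for 10% to 40% other stops, under constant hazards and no administrative censoring. At n=200 and few other-reason stops it is small beside sampling error.

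Dose reduction is the more exposed endpoint. TEAE stops without a prior reduction also compete, no crude table is listed, and the event itself is not fully defined. The change is worth making because it is cheap and fits an incidence-based primary endpoint, not because the planned curves are shown to be seriously misleading.

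**What to change.** In SAP 9.1 and displays 14.3.2.10 to 14.3.2.11, report Aalen-Johansen cumulative incidence:

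- **TEAE discontinuation.** The competing event is individual permanent discontinuation for a non-TEAE reason, or death not due to a TEAE, dated at last dose. A stop or death due to a TEAE counts as the event.
- **Dose reduction.** The competing event is permanent discontinuation without a prior reduction. State whether the protocol-mandated move to 400 mg BID and tapering at discontinuation count as reductions in this analysis.
- **Administrative censoring.** Keep it for sponsor termination, access by another mechanism and Week 144, as far as the recorded reasons allow the split.
- **If Kaplan-Meier is kept,** label it a net probability and show the cumulative incidence beside it.

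The cost is minor programming (an event code in the SAS procedure) and wording, including the matching Kaplan-Meier text in Protocol 14.3.5 and both synopses. Protocol 7.4.1 already requires the reason for discontinuation in the eCRF. SAP 8.1.4.3 says lack of efficacy was not captured as a reason. That does not block the change, since all individual non-TEAE stops form one category, but the coding of administrative reasons should be checked first.

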#### 9.1.1. Events of Special Monitoring

EOSMs for this study include hemolysis, SARS-CoV-2 infections (asymptomatic and symptomatic),

Time to each subject's first SARS-CoV-2 infection,

will be estimated separately using the Kaplan-Meier method. The results will be displayed in summary tables as well as in a Kaplan-Meier plot. Subjects who do not experience the event will be censored at the date of the most recent dose of BCX9930.

Duration of SARS-CoV-2 infection will be summarized as well as displayed in a Kaplan-Meier plot, with the event as the unit of interest rather than the subject. Ongoing durations will be censored at the most recent examination date. The summary display will provide the median duration of event by treatment category.

These summaries and plots will be presented by treatment category.

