11.3.7. End of Study Visit

Subjects who permanently discontinue treatment will return to the clinic for the hemolysis monitoring visits detailed in Section 11.3.5. Subsequently they will return to the clinic 3 weeks (21 ± 3 days) after the date of their last dose of BCX9930 for their end-of-study assessments.

The following assessments will be performed at the end of study visit:

- Subject weight
- Targeted physical examination
- Vital signs (BP, temperature, and pulse rate)
- 12-lead ECG
- Blood collection for clinical chemistry, hematology, coagulation
- Urine collection for urinalysis with microscopy, urine pregnancy test for female subjects of childbearing potential
- Urine collection for biomarker testing
- Disease-specific assessments:
 - Assessment of PNH symptoms (fatigue, dyspnea, chest pain/discomfort, difficulty swallowing (esophageal pain), abdominal pain, headache, erectile dysfunction, hemoglobinuria, jaundice)
 - Review of blood transfusions
- PD blood sample
- Review of concomitant medications and AEs
- Study drug accountability (for early withdrawal visit only)

If an AE is ongoing at the end-of-study visit, additional clinic visit(s) or telephone contact(s) may be warranted (see Section 13.9.3).

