13.7. Monitoring for Hemolysis at Discontinuation of BCX9930

By inhibiting the alternative pathway of complement, the factor D inhibitor BCX9930 may improve hemoglobin levels by reducing the hemolysis of PNH RBCs. Thus, following discontinuation of BCX9930 treatment, subjects may be at risk of serious hemolysis.

Based on available data regarding the PK and PD of BCX9930, serious hemolysis, if it occurs, would be expected to present within days after discontinuation of therapy, therefore when subjects stop study drug therapy, either at the scheduled end of treatment or on premature discontinuation, they must be monitored for hemolysis, as described below. Samples may be analyzed at a local laboratory.

Hemolysis will be monitored by daily laboratory assessment of LDH, hemoglobin, complete blood count (CBC), and serum chemistry (serum creatinine, blood urea nitrogen [BUN]), along with vital signs and a targeted physical examination, for at least 3 consecutive days after discontinuing BCX9930. Sample(s) for PD biomarker analysis and PK will be collected 48 hours after the last dose of BCX9930.

Following the 3 days of monitoring, additional laboratory monitoring may be necessary, based upon the safety assessment of the Investigator and the Sponsor Medical Monitor.

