13.9.2. Recording Adverse Events

AEs spontaneously reported by the subject and/or in response to an open question from the study personnel or revealed by observation will be recorded during the study at the investigational site. Only clinically significant changes from baseline in protocol-mandated assessments such as vital signs, laboratory values, and ECGs should be reported as AEs. Information about AEs and SAEs will be collected from the signing of consent form until the end of the study. The AE term should be reported in standard medical terminology and as a diagnosis (not symptoms) when possible. For each AE, the Investigator will evaluate and report the onset (date and time), resolution (date and time), severity, causality, action taken with study drug, seriousness, and outcome,

Severity will be assessed by the Investigator using the DMID scale.

It is important to distinguish between serious and severe AEs. Severity is a measure of intensity, defined in Section 13.9.1.5, whereas seriousness is defined by the criteria under Section 13.9.1.2. An AE of severe intensity may or may not be considered serious.

Should a pregnancy occur, it must be reported and recorded on BioCryst's pregnancy form. Pregnancy is not regarded as an AE unless there is a suspicion that an investigational product may have interfered with the effectiveness of a contraceptive medication.

The outcome of all pregnancies (spontaneous miscarriage, elective termination, normal birth, or congenital abnormality) must be followed up and documented, even if the subject was discontinued from the study.

All reports of congenital abnormalities/birth defects are SAEs. Spontaneous miscarriages, elective abortions, and still-births should also be reported and handled as SAEs.

13.9.3. Method, Frequency, and Time Period for Detecting Adverse Events and Reporting Serious Adverse Events

Reports of all AEs and SAEs, regardless of Investigator attribution, are to be collected from the time of signing of the informed consent. All AEs and SAEs are to be reported on the AE eCRF.

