## 5.7.8. Treatment-Emergent Adverse Events

An AE is considered treatment-emergent if its start date and time is on or after the date and time of first on-study dose of study drug. If the AE start date is missing and the AE stop date and time is after the start date and time of the first on-study dose of study drug (or the AE is ongoing) then the AE will be considered treatment-emergent. If either or both times are missing, then dates alone will be compared. See Section 5.7.11 for incomplete dates or times.

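### The special-monitoring time-to-first-event curves censor at last dose but set no end date for events, so the tail is biased upward and can jump to 100%

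*SAP*

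**What the plan says.** SAP 9.1.1 plans separate Kaplan-Meier estimates, by treatment category, for special-monitoring events. The one visibly named is "Time to each subject's first SARS-CoV-2 infection". Its censoring rule is "Subjects who do not experience the event will be censored at the date of the most recent dose of BCX9930". The list of further events in that section is blacked out. SAP Table 7 lists Kaplan-Meier tables and plots for first creatinine above the upper limit of normal and for first potential drug-induced liver injury.

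The SAP bounds events only from below. In SAP 5.7.8 an adverse event qualifies if "its start date and time is on or after the date and time of first on-study dose of study drug". SAP 9.2.1 treats a graded laboratory abnormality as emergent if it appears after study drug starts and is at least one grade worse than baseline. Neither definition has a last-dose limit.

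Data continue after last dose. Protocol 13.9.2 says: "Information about AEs and SAEs will be collected from the signing of consent form until the end of the study". Protocol 13.7 requires daily laboratory checks, including serum creatinine, "for at least 3 consecutive days after discontinuing BCX9930". Under Protocol 11.3.7, "they will return to the clinic 3 weeks (21 ± 3 days) after the date of their last dose of BCX9930", and that visit includes clinical chemistry.

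SAP 9.1 covers time to dose reduction, time to discontinuation for an adverse event, and time to drug-related rash. It uses a different rule: "Subjects who do not experience a particular event will be censored at the date of the last study visit".

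**The concern.** Kaplan-Meier estimation needs censoring that does not depend on the outcome. Under 9.1.1 as written, two subjects who stop on the same day are treated differently according to what happens next. The one who stays event-free leaves the risk set at last dose. The one who has an event ten days later stays in until that day. After last dose, being at risk and having the event are the same thing.

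Treatment is capped at 144 weeks, so completers' last doses cluster around Day 1009. Just beyond that point the risk set can fall to a single subject, whose event takes the curve to 100%. Safety is the primary endpoint, and a reader of such a plot could take the final step as a real cumulative incidence.

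**Working it through.** The plan states no event rate, event count or power for these curves, so there is no figure to reproduce. The check applies the product-limit formula, F(t) = 1 − ∏(1 − d/n), with d events among n at risk.

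**Inputs from the documents.** Treatment lasts up to 144 weeks (1,008 days); the Week 144 visit is Day 1009 ± 6; the end-of-study visit is 21 ± 3 days after last dose; about 200 subjects are planned; there are two treatment categories; 15 subjects rolled over from Study 101 Part 3.

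**Assumed.** Event rates, the share completing, and the spread of last doses.

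**1. One late event.** All subjects complete, with last doses on Days 1003 to 1015. One subject has an event on Day 1019.
- SAP rule: n = 1, so F = 1 − (1 − 1/1) = 100% at every group size from 8 to 200.
- Censoring at last visit: F = 1/N, which is 12.5% (N = 8), 6.7% (15), 2.0% (50), 1.0% (100) and 0.5% (200).
- N = 100 with 10 earlier on-treatment events: the SAP rule gives 1 − 0.90 × (1 − 1/1) = 100%. Last-visit censoring gives 1 − 0.90 × (1 − 1/90) = 11%. Counting on-treatment events only gives 10%.
- An early stopper with an event on Day 510 while 99 others are at risk: F = 1/100 = 1.0%, so no distortion.

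**2. How often the curve ends at 100%.** Take N = 100, 15% on-drug incidence over 144 weeks and 70% completing. About 100 × 0.70 × 0.85 = 59.5 subjects reach the end event-free. With last doses over Days 1003 to 1015, a subject's last dose falls on average 6 days before the latest one. About 15/21 = 0.71 of post-dose events then fall after everyone else's last dose. For post-dose risk p, the chance is roughly 1 − exp(−59.5 × p × 0.71).
- p equal to the on-drug rate, 1 − 0.85^(21/1008) = 0.34%: exponent 0.14, chance 13%. Simulation gives about 10%, and 10% to 14% across repeat runs.
- p = 1%: exponent 0.425, chance 35%. Simulation gives about 33%.
- p = 3%: exponent 1.275, chance 72%. Simulation gives about 73%.

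At the on-drug rate, simulation gives about 27% at N = 200 and 2% to 3% at N = 15. With staggered stopping at N = 100 it gives about 1% to 6%.

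A second simulation has everyone completing, N = 100 and constant rates of 0.02, 0.1 and 0.2 per year:

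| Rate per year | True incidence | Mean final estimate, SAP rule | Mean, last-visit censoring | SAP curve ends at 100% |
|---|---|---|---|---|
| 0.02 | 0.055 | 0.132 | 0.056 | 8% |
| 0.1 | 0.246 | 0.454 | 0.248 | 27% |
| 0.2 | 0.431 | 0.646 | 0.434 | 37% |

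Last-visit censoring never ended at 100% here. With stopping spread over Days 200 to 1009, the SAP-rule means fall to 0.060, 0.264 and 0.461, against 0.054, 0.243 and 0.432 with last-visit censoring.

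**3. Before the tail.** At Day 1002 (N = 200, 15% on-drug, 30% stopping early, 3% post-dose), the SAP rule gives 15.76%, last-visit censoring 15.66%, and cutting both events and censoring at last dose 14.82%. The mismatch itself is worth 15.76 − 15.66 = 0.10 point. The other 15.66 − 14.82 = 0.84 point comes from whether post-dose events are counted at all.

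**The case against.** The strongest reply is that an on-treatment analysis was intended, with post-dose events left out. That may be so, and the blacked-out text could hold a qualifier. But nothing visible says it, and the definitions in 5.7.8 and 9.2.1 point the other way. Either reading needs a sentence.

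Several stronger readings are tempting, and the documents do not support them.
- **That almost every curve will end at 100%.** A figure near 92% needs one pooled curve of 200 and 3% post-dose events. The SAP plots by category, and 3% is about nine times the on-drug rate for 21 days (3/0.34). No document supports that for SARS-CoV-2.
- **That the whole curve is materially wrong.** When most subjects complete, the gap at Day 1002 is about 0.1 point. A gap near 0.9 point mostly reflects dropping post-dose events.
- **That the rule certainly governs the creatinine and liver-injury curves.** This is plausible from Table 7 but inferred.
- **That daily post-stop tests would pick up liver events.** The discontinuation panel in Protocol Table 5 has no ALT, AST or bilirubin; chemistry returns at the 3-week visit. Protocol 13.7 also describes hemolysis after stopping as a possibility, not an expectation.

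It is also fair that many subjects may not reach Week 144, since access elsewhere or a sponsor decision can end treatment sooner. That makes the jump rare. No decision rule uses these curves, SAP 3.3 emphasizes estimation over testing, and the individual data are listed.

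**Conclusion.** The point stands as a defect in the tail of the time-to-first-event curves in SAP 9.1.1. Followed as written, membership of the risk set after last dose depends on having the event, so the tail is biased upward. The curve reaches 100% if a late event falls after every other last dose in its category.

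The mechanism follows from the text; its frequency rests on assumptions. With 15% on-drug incidence, 70% completing and N = 100, it is about 10%, 33% or 73% of curves for post-dose risk equal to the on-drug rate, 1% or 3%. With staggered stopping it is about 1% to 6%. Confidence is high for the SARS-CoV-2 curve and lower for creatinine and liver injury. The SARS-CoV-2 duration curve has its own censoring date and is not affected. It should be corrected, but it does not threaten the study's conclusions.

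**What to change.** In SAP 9.1.1, give events and censoring the same end of risk period and state it. Either option works:
- count first events up to the last study visit and censor event-free subjects there, in line with 9.1; or
- count first events only up to last dose, or last dose plus a stated window, and censor at that same limit or at last visit if earlier.

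Name every curve the rule covers, and print numbers at risk under each plot so that a thin tail is visible.

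As a minor consistency point, time to dose reduction and time to discontinuation in 9.1 should be censored at last dose, because a subject who has stopped drug can no longer have either event. The effect of the present rule there has not been quantified; it adds about three weeks at risk.

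The cost is one or two sentences in 9.1.1 and one in 9.1, plus a programming change. No new data are needed.
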